The overall goal of this project is to provide feasibility data for a novel method of defining patient-specific functional anatomic targets for GPi DBS placement.

Aim 1. To evaluate the feasibility of a novel, clinically applicable 3 Tesla (3T) MRI protocol for functional segmentation of the GPi based on connectivity measures derived from MRI diffusion-weighted imaging.

- a) Assess the ability of spatially localizing the motor functional representation within the GPi in individual subjects with a clinically feasible imaging protocol using widely available 3T MRI.

Aim 2. To determine the variation in degree of overlap between the traditional atlas-based target point and the derived MRI functional segments on pre-operative imaging

- a) To better understand the relationship of the traditional target point and the functional segments, we will compare the degree of overlap. We hypothesize that the traditional target point will show variation between subjects in the degree of overlap with each functional segment suggesting inadequacy of structural targeting methods that are based on generalizations rather than patient-specific functional targets

Aim 3. To compile preliminary evidence for the role of a patient-specific, functional-based targeting protocol to replace potentially inaccurate atlas-based methods in treating Parkinson's disease that can be implemented on commonly available 3T MRI scanners

- a) Based on the stimulation parameters used to achieve a satisfactory treatment response, a model of the volume of activated tissue will be generated. The degree of overlap between this volume of tissue will be assessed on both the pre-operative functional target and the original atlas-based target. We hypothesize that the volume of activated tissue will closely overlap with the functional segment most connected to the motor and pre-motor cortex.
- b) Current data will be the basis for pursuing additional funding for implementing the 3T protocol in a larger patient cohort to further explore the potential role in treatment targeting
- c) Eventual long-term goal will be acquisition of external funding for a clinical trial using the targeting sequence prospectively to assess the overall goal of this investigation: improving success rate and decreasing complication rate by addition of patient-specific functional targeting of the GPi.

II. Background and Significance

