Parkinson's disease (PD) is a common, debilitating neurologic disease. Over one million people suffer from PD in the United States alone. Deep brain stimulation (DBS) has been shown to be an effective treatment option. One of the most frequent targets for DBS in PD is the globus pallidus internus (GPi).

One limitation of surgical (e.g., DBS) treatment for PD is the inability to identify functional brain targets pre-operatively. Current methods rely on atlas-based approaches or coordinate-based stereotaxy where a specific coordinate, based on larger landmarks, is presumed to be the approximate location of the targeted functional region in all patients. These targeting methods rely on standardized coordinates that do not account for known inter-individual variations in functional anatomy. In fact, it has been previously reported that 46% of patients

with poor response to DBS therapy have malpositioned DBS leads.² There is also disagreement in the choice of ideal atlas-based coordinates. Perhaps most concerning regarding all methods of structural localization is the assumption that brain function is predictable by brain structure. The validity of such assumption is questionable as it has been shown that brain functional localization may vary significantly from predictions based solely on structure. It is now well-known that pathologic changes in the brain can result in variations in the relationship of structure and function due to neural plasticity.

The idea of brain connectomics is a rapidly developing field of neuroscience. The ability to examine *in vivo* human brain functional connectivity has revealed new insight into many neurologic and neuropsychological conditions. To date, the clinical impact of connectomics has been limited. The origin of the current proposal was the belief that this emerging technology could be applied to a very specific problem in clinical medicine not well-addressed by current techniques. As such, this project would ideally serve as a model and further proof that such science can be currently translated into clinical medicine.

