a. Study Design or Overview - Patients selected to undergo GPi DBS placement will be eligible for enrollment in the study. In addition to standard-of-care tests, subjects will undergo an MRI consisting of the proposed novel imaging protocol prior to placement of DBS. The patient will subsequently undergo standard-of-care therapy for DBS placement. Once the stimulator has been programmed post-operatively, the stimulation parameters and corresponding clinical changes will be collected and used to model the volume of activated tissue. The patient will additionally undergo a follow-up MRI used to localize the electrode within the brain to further localize the volume of activated tissue.

b. Study Subjects - Patients presenting to Mayo Clinic Neurosurgery identified to undergo deep brain stimulator placement in the GPi will be identified as potential subjects. Exclusion criteria for the proposed study would be any patient with contraindication to 3 Tesla MRI.

c. Sample Size - Due to the lack of any adequate preliminary studies, a sample size is estimated without statistical basis. A sample size of ten was chosen based on expected recruitment possibilities and sufficient size to prove feasibility and estimate power size for subsequent studies.

d. Data Collection -

Pre-Operative: Relevant clinical information will be collected including demographic data (age, gender), duration of Parkinson's disease, medication history, and a Unified Parkinson Disease Rating Scale (UPDRS) score. Pre-operative MRI will consist of a robust, multi-shell diffusion sequence at high resolution (1.5 x 1.5 x 1.5 mm voxel; b =1000, 2000; 64-directions, AP and PA phase encoding). Additional routine structural imaging consisting of T1-weighted MP-RAGE and FGATIR will also be obtained for purposes of identifying targets for segmentation.

Post-Operative: Clinical data will consist of post-treatment UPDRS score, complications related to DBS placement (e.g. infection, hemorrhage), and the stimulation parameters (voltage and contacts used) from the DBS programming to go with the tremor scoring. Stimulation parameters will also be recorded for any DBS programming that resulted in adverse effects, as well as the effect elicited. The patient will undergo an additional post-operative MRI using a T1 MP-RAGE sequence for purposes of localizing the final lead position.

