e. Data Handling - All data will be collected in an anonymized fashion with unique coded identifiers for each subject. The identifier linking to the patient will be stored in a separate password-protected spreadsheet for purposes of collecting data at each of the timepoints in the study.

Clinical data will be tabulated within an Excel spreadsheet that is also password protected and recorded by anonymized ID. The imaging data will be downloaded from the MRI scanner on an encrypted drive and transferred to a password-protected and encrypted Mayo Clinic computer only accessible to the PI. Imaging data will be collected and stored without patient identifiers, only by unique study ID. Processing of the imaging data will be performed and saved on the computer.

f. Data Analysis - MP-RAGE structural scans will be coregistered to the diffusion data and automatically segmented into regions of interest using FreeSurfer software. Regions of interest will consist of: (1) prefrontal cortex, (2) supplementary motor area, (3) premotor cortex, (4) primary motor cortex, (5) putamen, (6) caudate, (7) thalamus, (8) globus pallidus externus, (9) pedunculopontine nucleus, and (10) subthalamic nucleus.

The diffusion data will be used to determine voxel-wise diffusion parameters using a Markov Chain Monte Carlo sampling in the FMRIB Software Library (FSL) “bedpostx” function. A multi-fiber approach (2 fiber orientations) using a multi-shell model will be used. To perform GPi segmentation based on structural connectivity, we will utilize a probabilistic tractography method by way of FSL’s “probtrackx” to calculate probability of connection of each GPi voxel to the predefined volumes of interest (above). Each GPi voxel will then be assigned to the one target with the greatest number of propagated paths by using FSL’s “find_the_biggest” function.

Using the MP-RAGE and FGATIR MRI data, the target point for DBS placement will be determined using current standard of care. The amount of overlap between this target and each of the GPi functional segments will be calculated.

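### If the analysed target is a standardized coordinate, differences in GPi position alone can produce the overlap variation that Aim 2a reads as a case for functional targeting, and IV.f cannot separate the two causes

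*Combined protocol and SAP*

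**What the plan says.** Aim 2 (section I) is "To determine the variation in degree of overlap between the traditional atlas-based target point and the derived MRI functional segments on pre-operative imaging". Aim 2a hypothesises that "the traditional target point will show variation between subjects in the degree of overlap with each functional segment suggesting inadequacy of structural targeting methods", and describes these methods as ones "that are based on generalizations rather than patient-specific functional targets".

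Section II (Background and Significance) describes current targeting as one in which "a specific coordinate, based on larger landmarks, is presumed to be the approximate location of the targeted functional region in all patients". It then states the wider premise under challenge: "Perhaps most concerning regarding all methods of structural localization is the assumption that brain function is predictable by brain structure".

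Section IV.f (Data Analysis) defines the analysed target in one sentence: "Using the MP-RAGE and FGATIR MRI data, the target point for DBS placement will be determined using current standard of care". The whole Aim 2 analysis is the next sentence: "The amount of overlap between this target and each of the GPi functional segments will be calculated". There is no comparator, the target is not expressed relative to the patient's own GPi, and the variation is not divided by source. The scans needed to outline the GPi are already planned; IV.d says "Additional routine structural imaging consisting of T1-weighted MP-RAGE and FGATIR will also be obtained".

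**The concern.** A landmark-based point can meet different segments in different patients for two reasons:

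1. The GPi, as a visible structure, lies elsewhere relative to the landmarks.
2. The borders between functional segments lie elsewhere within the GPi.

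Only the second bears on whether function can be predicted from structure. The first could be addressed by locating each patient's GPi on structural MRI, without tractography. Aim 2a contrasts a generalised coordinate with a functional map and leaves out this third possibility.

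The pilot is meant to support funding for a larger trial of functional targeting. If variation is expected even when all functional maps are identical, observing it says little about whether a functional map adds anything to patient-specific structural localisation.

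**Working it through.** **No plan figure to reproduce.** The sample size of ten is stated to have no statistical basis. The documents give no GPi dimensions, target volume or size of positional variation. All geometry below is therefore assumed.

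**Model.** The GPi is an ellipsoid and the motor segment is the part on one side of a plane fixed within it. The target is a sphere whose centre, with no shift, lies at t0 in the GPi's own frame. For patient i, a relative displacement d_i is drawn as normal, mean 0, SD s on each axis. Then

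O_i = volume of (sphere centred at t0 + d_i, within the motor segment) / volume of the sphere.

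The functional map is the same in every patient, so any spread in O_i comes from position alone.

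**Geometry A:** semi-axes 3 x 7 x 5 mm, split in half across the 7 mm or the 5 mm axis; sphere radius 1.5 mm; centre 2-3 mm inside the motor half.

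**Geometry B:** semi-axes 3 x 6 x 3.5 mm, split across the 6 mm axis; centre 2 mm inside the motor half; sphere radius 0.75, 1.5 or 2.5 mm.

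| s (mm per axis) | A: SD of overlap | B, radius 1.5 mm: SD | B, radii 0.75-2.5 mm: SD | B, radius 1.5 mm: median range in 10 patients |
|---|---|---|---|---|
| 0 | 0 | 0.00 | 0.00 | 0.00 |
| 0.5 | 0.01-0.05 | 0.02 | 0.01-0.06 | 0.02 |
| 1.0 | 0.12-0.22 | 0.17 | 0.16-0.17 | 0.43 |
| 1.5 | 0.29-0.34 | 0.33 | 0.25-0.37 | 0.94 |
| 2.0 | 0.37-0.38 | 0.37 | 0.28-0.44 | 0.99 |

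A split across the thin 3 mm axis is left out: a centre at 2 mm with radius 1.5 mm reaches 3.5 mm, already beyond the 3 mm edge before any shift.

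**The opposite case.** In geometry B (radius 1.5 mm), hold GPi position fixed and move only the functional border. A border SD of 1 mm gives an overlap SD of 0.13 (median range in ten patients 0.26). A border SD of 2 mm gives 0.32 (0.97). These spreads are of the same order as the positional ones, so the size of the variation does not identify its cause.

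**The two sources do not add.** In the same setting, position alone at 1.5 mm gives SD 0.33 and border alone at 2 mm gives 0.32. If variances added, the total would be sqrt(0.33² + 0.32²) = sqrt(0.2113) = 0.46. The simulated total is 0.37, because overlap is bounded between 0 and 1. The two sources can be shown side by side, but subtracting one variance from the other would mislead.

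**Points outside the GPi.** In geometry A, of the target centres that miss the motor segment, about half or more lie outside the GPi altogether at s = 1.5 mm, and about two thirds or more at s = 2 mm.

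**The case against.** The strongest objection is the IV.f sentence on how the target is set. It uses the patient's own MP-RAGE and FGATIR. If standard of care includes adjusting the point to the GPi seen on those scans, most of the positional difference is removed before overlap is calculated. At a residual of 0.5 mm the effect nearly vanishes, with SD about 0.01-0.06 over both geometries. This stands. A reader might infer that Aim 2 is bound to find variation whatever the functional anatomy. The documents do not support that, because they leave open whether the point is a fixed coordinate or an adjusted one.

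Secondly, IV.f calculates overlap with every GPi segment. A target partly outside the GPi would show as segment overlaps summing to less than the whole target. This also stands: the larger positional misses could be recognised from planned data. However, the plan does not say that the shortfall will be reported or used, and it does not identify shifts that stay inside the GPi.

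Thirdly, this is a ten-patient feasibility study, Aim 2 is largely descriptive and its hypothesis says only that variation is suggestive. Variation of a generalised coordinate does bear on the narrower statement that one coordinate does not suit everyone. That is fair and limits the weight of the point. It does not rescue the contrast with functional targets. Aim 3 and the regression in IV.f do not fill the gap either: they relate activated-tissue overlap to clinical change and do not address why the target's overlap varies.

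**Conclusion.** The point holds conditionally. If the analysed target is a standardized coordinate, positional differences of about 1 mm SD per axis or more can produce appreciable overlap variation (SD 0.12-0.22 at 1 mm, rising to 0.37-0.38 at 2 mm in geometry A) with no functional variation at all. If the point is already adjusted to the visible GPi, the effect may be negligible. These sizes rest on assumed GPi shape, target volume and shifts. The qualitative result does not depend on the exact values: position alone can generate variation, and in the model fixing the point relative to the GPi removes that part.

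A reader might also infer that whatever remains at a GPi-relative point is functional. The documents do not support that. The remainder would also contain tractography and segmentation error and differences in GPi shape. The Background reports inconsistent segmentation in the one earlier study in normal subjects, and no repeat pre-operative diffusion scan is planned from which to estimate that error.

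This is a fault of interpretation and a missing comparator. It is not a calculation error and does not affect the feasibility aim.

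**What to change.** First, reconcile Aim 2 and section II with IV.f: state whether the analysed target is a standardized coordinate or one adjusted to the visible GPi, and what volume it is given for the overlap calculation.

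Then add to IV.f, for each GPi:

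- (a) the fraction of the target lying outside the patient's own GPi;
- (b) the overlap with each segment for a second point, placed at one common GPi-relative position on the patient's MP-RAGE/FGATIR outline (for example, the group-mean position as a fraction of the GPi extents). This point is for analysis only and guides no lead;
- (c) individual values and between-subject variation for both points side by side, without subtracting variances.

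Limit the Aim 2a conclusion accordingly. Report variation that disappears at the GPi-relative point as structural. Describe what remains as an upper bound on functional variation that also contains segmentation error and GPi shape differences.

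The cost is a change of wording and one more calculated point per GPi. It needs no new scans, since the structural images are already planned and the tractography already requires a GPi region. The downside is that the Aim 2 result may look less favourable to functional targeting.

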The postoperative MRI scan will be coregistered to the pre-operative scans. The final location of the DBS lead will be calculated using LEAD-DBS software. Based on the stimulation parameters, the volume of activated tissue will be calculated with respect to lead localization. The amount of overlap between the volume of activated tissue (VAT) and each GPi segment will be calculated. Linear regression analysis will be performed to determine the degree of improvement in tremor score and degree of overlap between the VAT and each GPi segment. We hypothesize greater overlap between the VAT and GPi segment maximally connected to the primary motor cortex will result in a greater improvement in clinical improvement.

g. Feasibility and Time Frame – The expected timecourse for the study is one year. We would anticipate ~25 patients per year to be potential subjects based on historical figures of number of GPi DBS placements done at Mayo Clinic Florida. The timetable for each individual subject should be <6 weeks. Processing time for each subject is expected to be ~1 week. Since the study is incorporated into current standard-of-care clinical workflow (e.g.

imaging prior to surgery and followup imaging at time of return clinical visit), we anticipate high subject retention.

h. Strengths – The strength of the study lies in the robust diffusion sequence obtained by way of the recently released “multiband” diffusion MRI sequence. This allows a substantial improvement in resolution and data quality compared to traditional methods. Additionally, the prospective nature allows us to collect not only optimal therapeutic DBS stimulation parameters, but also those which produce unintended side effects. By capturing this additional data, it will help us to shed light on the cause of these unintended effects and potentially improve the pre-operative functional targeting. Lastly, the significant experience of the investigators in functional neuroimaging and deep brain stimulation is a significant benefit in preparing the study design and interpreting the data.

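### Aim 2a reads between-subject variation in target overlap as a sign that structural targeting is inadequate, but spread alone cannot support that; the level of motor-segment overlap is needed

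*Combined protocol and SAP*

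**What the plan says.** Aim 2 (I. Specific Aims) is "To determine the variation in degree of overlap between the traditional atlas-based target point and the derived MRI functional segments on pre-operative imaging". Aim 2a adds the interpretation: "the traditional target point will show variation between subjects in the degree of overlap with each functional segment suggesting inadequacy of structural targeting methods".

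In IV.f Data Analysis, GPi voxels receive hard labels: "Each GPi voxel will then be assigned to the one target with the greatest number of propagated paths". For the planned target, the same section says only that "The amount of overlap between this target and each of the GPi functional segments will be calculated". It gives no summary statistic, no reference level and no rule for reading the result.

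The one planned analysis against a clinical outcome, also in IV.f, is a linear regression concerning the "degree of improvement in tremor score and degree of overlap between the VAT and each GPi segment". Its predictor is overlap of the volume of activated tissue (VAT), not of the planned target. Aim 3a has the VAT "assessed on both the pre-operative functional target and the original atlas-based target", but this does not feed into the Aim 2a conclusion.

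The motor segment is described in two ways. Aim 3a refers to "the functional segment most connected to the motor and pre-motor cortex", while the closing hypothesis of IV.f names the primary motor cortex only. The region list in IV.f keeps supplementary motor area, premotor and primary motor cortex separate.

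**The concern.** Whether a target is adequate depends on where it lies relative to the motor segment, and finally on whether that position matters to patients. The spread of overlap between patients answers neither question. Ten targets can vary while all lie mainly in the motor segment, and they can vary equally while all lie mainly outside it. A conclusion drawn from spread reads the same in both situations.

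What is at stake is interpretation. The pilot is meant to support a larger study (Aims 3b and 3c; II. Background and Significance). A finding of inadequacy that would be reached under good and bad targeting alike adds nothing to that case, while the informative quantity, the level, is calculated and left unused.

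**Working it through.** The plan has no figure to reproduce. IV.c states that the sample size of ten has no statistical basis, and no alpha, power, effect size or SD is given. The check is therefore of the logic, with n = 10 from the protocol and all overlap values assumed for illustration.

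**1. Target treated as a point (hit or miss).** The plan speaks of a target point, defines no target volume and uses hard labels, so each patient's overlap may be 0 or 1. With a proportion p of hits, SD = sqrt[(10/9) × p × (1 − p)]. The formula is unchanged when p and 1 − p are exchanged. The interval is the exact (Clopper-Pearson) one.

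| Targets in motor segment | SD | Level, exact 95% CI |
|---|---|---|
| 0/10 | 0.000 | 0 to 30.8% |
| 2/10 | sqrt(1.111 × 0.16) = 0.422 | 2.5 to 55.6% |
| 8/10 | sqrt(1.111 × 0.16) = 0.422 | 44.4 to 97.5% |
| 10/10 | 0.000 | 69.2 to 100% |

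The SD column cannot tell the first row from the last, or the second from the third. The level separates the extremes clearly. 2/10 and 8/10 have distinct estimates, but their intervals overlap at this sample size.

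**2. Target treated as a volume (continuous overlap).** Take ten motor-segment overlaps of 0.70, 0.72, 0.75, 0.80, 0.85, 0.88, 0.90, 0.95, 0.97 and 1.00. The mean is 0.852 and the SD 0.107. Replace each value x by 1 − x: the mean becomes 0.148 and the SD stays 0.107. Mostly-good and mostly-bad targeting give identical spread.

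**3. How likely is some variation?** In simulated studies of ten patients with beta-distributed overlap, a range above zero occurred in 100% of replicates, both with mean 85% (SD 5 or 10 points) and with mean 5% (SD 2 or 3 points). This holds for any continuous measure. Segmentation error adds to it: with an identical true overlap of 0.85 in every patient and an assumed error SD of 0.05, 0.10 or 0.15, the median observed SD is 0.048, 0.091 or 0.125. No repeat pre-operative scan is planned that would separate error from true variation.

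**4. Would a regression of improvement on target overlap settle adequacy?** The criterion checked is a 95% CI for the slope that excludes zero, at n = 10, with bivariate normal data.

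- Power is about 32% at a correlation of 0.5 and 68% at 0.7.
- An observed correlation of 0.5 has a Fisher-z 95% CI of tanh(0.549 ± 1.96/√7) = −0.19 to 0.86.
- Suppose there is a real effect, with a slope giving correlation 0.7 when overlap has SD 25 points. If all targets miss similarly (mean 5%, SD 2 to 3 points), the interval excludes zero in the expected direction in only 4 to 5% of studies. If every overlap is 0, the slope is undefined.

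A slope also needs spread, so it cannot detect a uniform miss.

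**The case against.** The strongest reply is that Aim 2a states a hypothesis in soft terms, in a ten-patient feasibility study. It sets no threshold, test or decision. IV.i already warns that results may not be significant, outcome testing is deferred to a later trial, and V. Human Subjects says the data do not guide care. All of this stands, and it limits the point to interpretation. It does not repair the inference, because soft wording still attaches inadequacy to a quantity that cannot indicate it.

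A second reply is that IV.f makes the levels available, that Aim 3a checks the atlas target against a treatment-linked volume, and that regressing on the VAT, the tissue actually stimulated, is defensible. This is also fair. What is missing is any use of the level, or of Aim 3a, in the Aim 2a conclusion.

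A reader might go further and infer that the Aim 2a reasoning stays silent when every target misses. The documents do not support that. With any non-zero variation counted, a continuous overlap varies even when all targets miss. Because Aim 2a covers each segment, misses scattered over different non-motor segments also show variation. Silence requires that all targets miss in essentially the same way, or a minimum range that the protocol does not contain.

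A reader might also infer that the plan should have tested adequacy by regressing improvement on target overlap. Step 4 of the working shows why that test would fail too.

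**Conclusion.** The point holds as a flaw in a stated inference. Between-subject variation in target overlap is close to certain on a continuous scale, and its size does not separate mostly-good from mostly-bad targeting: SD 0 for both 0/10 and 10/10 hits, and 0.42 for both 2/10 and 8/10. The hit/miss result is exact. The continuous examples, error SDs and simulation settings are assumptions, used only to show the mechanism.

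The point does not show that atlas targeting is adequate or inadequate. Nor does it show that the study would formally declare inadequacy, since no decision rule is given. It should be changed because the change costs little and alters what the pilot can legitimately conclude.

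**What to change.** - **Aim 2a:** limit the conclusion to describing anatomical variation, and state that variation is not by itself evidence of inadequacy.
- **IV.f, definition:** prespecify one motor segment, reconciling Aim 3a with the IV.f hypothesis, and say whether the target is handled as a point or a volume.
- **IV.f, reporting:** give each patient's atlas-target overlap with that segment, and the mean overlap (volume) or the proportion of targets inside it (point) with a 95% CI. Base any statement about targeting on this level, not on the spread.
- **Optional:** add a regression of improvement on target-motor overlap, labelled exploratory and reported as a slope with 95% CI. State that it is not a test of adequacy or inadequacy, that it is uninformative when all targets miss similarly, and that an interval including zero is inconclusive.

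The cost is a few sentences and a summary of overlaps already planned, with no new patients, visits or scans. The downside is a weaker Aim 2 conclusion and, at n = 10, wide intervals.
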